Serum collection for ADA (pre-dose if dosing visit)		Х		Х	Х	Х	Х	Х		Х	Х
Clinical laboratory sample collection 	X	Х		Х		Х		Х		Х	Х
Viral Serology 	X									Х	Х
Serum pregnancy, chorionic gonadotropin	X										
Urine Pregnancy Test 		X		X	X	Х	Х	X		Х	Х

Table 6:Part 2 Schedule of Events (Study RNX-AX204-101)1

Study Phase	Screening			Trea	atment P		Follow-Up				
			W	indow a	t Visits 3		± 7 days				
Study Day	-84	1	8	21	42	63	84	104	137	169	253/ET 
	through		(±3						Month 5	Month 6	Month 9
	-1		days)								
Visit Number	1	2		3	4	5	6	7		8	9
Urine sample for drug screen 	Х										
Urinalysis	Х	Х		Х		Х		Х		Х	Х
Prior and Concomitant Medications	Prior		Concomitant (On-going) Post-Trt								
Adverse Events 			Treatment-Emergent (On-going) Post-Trt								
Serious Adverse Events	Pre-Trt		Tr	eatment-l	Emergent	(On-goi	ng)			Post-Trt	

<sup>1 Abbreviations: ADA = anti-drug antibody, AE = adverse events, ECG = electrocardiogram, EDC = electronic data capture. ET = early termination. ID = identification, PK = pharmacokinetic, SAE = serious adverse event

benzodiazepines, methadone, and propoxyphene).

 Adverse Events are only collected upon the start of study drug. Events occurring prior to this are to be reported as part of the subject medical history. However, SAEs are to be collected from the time of informed consent.

<sup>2 MRIs will be run locally and findings read by a sponsor-arranged expert prior to subject enrollment into the study.

<sup>3 Telephone call to inquire about any AEs and determine if subject should come to clinic for evaluation.

<sup>4 Vital signs (blood pressure, pulse rate, respiratory rate or pulse oximetry, and oral body temperature) will be measured after the patient has been in a sitting or recumbent position for 5 minutes. Vitals will be taken pre-dose, post dose, then every 2 hours until subject leaves the unit

<sup>5 ECGs will be taken in triplicate, 5 minutes apart, and will be obtained after the patient has been in a supine (resting) position for at least 5 minutes. ECGs are taken pre-dose at visits where study drug is administered. ECGs will be read locally.

<sup>6 GRASSP prehension ability and prehension performance testing will be video recorded.

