### 11.1.5. Post Treatment Follow-up Visit 5 (Study Day 29/ET)

Visit 5 (Study Day 29/ET) is to be conducted on subjects who will be completing the study as well as those who terminate early or are withdrawn from the study.

At this visit, a full physical exam will be performed. The subject will be weighed and weight recorded on the eCRF. Vital signs (BP, pulse, respiratory rate or pulse oximetry, and oral body temperature) will be obtained. A urine pregnancy test will be obtained on all females of childbearing potential.

Subjects will undergo lumbar puncture for CSF collection for PK assessments. Blood sampling for laboratory testing including viral serology will also be obtained. Serum for PK and the presence of ADA will be analyzed. Urine sample will be obtained for urinalysis.

Information on changes or newly administered concomitant medications as well as any new or ongoing AEs will be recorded on the eCRF.

All scales should, if possible, be administered by the same clinician who administered the scales during the Screening period. These shall be completed in the order as noted in 11.2 and include the full ISNCSCI scale, SCIM III self-care and mobility scale, GRASSP, Modified Ashworth Scale, and autonomic evaluations as per ISAFSCI. Subjects will also be administered several questionnaires at this visit, including:

- BPI (Appendix 9)
- SF-36 v2 (Appendix 6)
- Neuro-QOL (Appendix 7)

Subjects' completion or termination from the study (in the case of subjects who terminate early from the study or who are withdrawn) will be recorded on the eCRF and in the subjects' record.

# 11.2. Part 2

Each investigator will be assigned a unique site code. This site code will be concatenated with the screening number to assure that each subject will be uniquely identified in the clinical database. Site numbering will begin with 01 preceded by the number 2, and screening numbers will begin with 001. As subjects are screened, the next subject qualified chronologically at a site will be assigned the next number in ascending numerical order. Thus, the subject identification number for the first subject screened at the first site will be 201-001. The first subject enrolled at the second site will be 202-001 and so on.

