During the lumbar puncture, an amount of CSF approximately equivalent to the amount of investigational product to be injected into the intrathecal space (~9-20 mL) will be obtained predose for CSF/PK assessment, spinal cord injury biobanking, and potentially biomarker analysis. For the 20 mL maximum dose, at least 15 mL of CSF should be collected immediately prior to administration. If at least 15 mL cannot be collected, the principal investigator may elect to skip dosing for the visit or to ask the subject to return on the following day for a second attempt after additional hydration. In this situation, the subject may be directed to remain at a nearby overnight accommodation or home (if within a reasonable distance) and report the next morning for examination or to remain in the hospital overnight. Note that, under these circumstances, there is no requirement for an overnight hospital stay; if a decision is made to keep the patient overnight for convenience (e.g. travel issues), this hospitalization should not initiate a serious adverse event report (e.g. local alternate accommodations not readily available). Investigational product will be administered via slow bolus infusion intrathecal administration. Details including dose and quantity administered, physician administering the investigational product, and date and time of administration will be recorded on the eCRF and in the subject's record. Post lumbar puncture and post-dose subjects are to be monitored for any adverse events.

The Site Principal Investigator may discontinue a subject from the study due to unsuccessful collection of CSF to allow for isovolumetric dose administration if the subject has not received any doses and they consider it unlikely that further dosing attempts will be successful. Subjects who received at least one dose of investigational product should complete the remaining visits to monitor for safety and efficacy as per the schedule of events. Under this circumstance, further per-protocol LP attempts should not be made. Conducting all LPs under fluoroscopy should be considered if difficulties in obtaining adequate CSF collection is encountered.

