## 14.1. Safety Parameters

Safety will be evaluated similarly for both Parts, through the collection of data from:

- Physical examinations
- Vital signs
- 12-lead electrocardiograms
- Laboratory parameters (hematology, blood chemistry, and urinalysis)
- Treatment-emergent adverse events (TEAEs).
  - TEAEs will be defined as any AE occurring during or after the injection of investigational product.
  - TEAEs will be limited to those events occurring within 28 days after the last visit.

Condition-specific safety outcomes will include:

- ISNCSCI, GRASSP and all of the neurological measures evaluated for efficacy
- Spasticity (Modified Ashworth Scale) [Pandyan 1999]. A clinician administered examination for spasticity which measures muscle tone changes. A score of 0-4 is assigned to each muscle group evaluated (Appendix 5). Notes: Testing will exclude fingers and thumb. Scores are to be recorded for left and right sides for each muscle group tested.
- Pain (BPI) [Cleeland 1994]. A self-administered questionnaire used to assess the severity of a subject's pain and the impact of this pain on the subject's daily functioning.

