#### 14.2.5. Adverse Event Reporting

The investigator is to record all directly observed AEs and all AEs spontaneously reported by the subject in the source documents and eCRFs.

All observed or volunteered AEs regardless of treatment arm or suspected causal relationship to the investigational product(s) will be reported as described in the following sections.

For all AEs, the investigator must pursue and obtain information adequate both to determine the outcome of the AE and to assess whether it meets the criteria for classification as an SAE requiring immediate notification to the sponsor or its designated representative. For all AEs, sufficient information should be obtained by the investigator to determine the causality of the AE. The investigator is required to assess causality. For AEs with a causal relationship to the investigational product, follow-up by the investigator is required until the event or its sequelae resolve or stabilize at a level acceptable to the investigator, and the sponsor concurs with that assessment.

In order to ascertain if headaches are secondary to the lumbar puncture per se, the clinical characteristics of the headache, including positional exacerbations will be assessed and reported. For Part 1, adverse events should be recorded and monitored from the time of first dose through subject completion of the study up to 28 days post-dose, or until the investigator deems the AE as resolved or stable (unchanging). Serious AEs should be recorded and monitored from the time of signing of the informed consent form (ICF) through subject completion of the study up to 28 days after completion of the study, or until investigator deems the SAE as resolved or stable (unchanging).

For Part 2, adverse events should be recorded and monitored from the time of first dose up to 28 days after completion of the study (28 days after Month 9 visit or ET), or until the investigator deems the AE as resolved or stable (unchanging). Serious AEs should be recorded and monitored from the time of signing of the informed consent form (ICF) through subject completion of the study (28 days after Month 9 visit or ET), or until investigator deems the SAE as resolved or stable (unchanging).

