6.2 Safety Population (Part 1 and Part 2)

The Safety Population will consist of all subjects treated with at least one dose of study treatment. Safety outcomes will be assessed using the Safety Population. For Part 2, safety outcomes, including the condition-specific safety outcomes as described in section 8.8.7, will be analyzed according to their actual treatment received.

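### Non-serious adverse-event recording is anchored to the dose rather than the lumbar puncture, so harm arising before the first dose, or after Day 29 from the last Part 1 puncture, goes uncounted, and the end rules conflict

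*Protocol*

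**What the plan says.** **Start of recording.** Protocol Table 5 footnote 13 and Table 6 footnote 12 carry the same rule: "Adverse Events are only collected upon the start of study drug", and then "Events occurring prior to this are to be reported as part of the subject medical history". Serious events are the exception and run from consent. For Visit 2 before dosing, sections 11.1.2 and 11.2.2 ask for new serious events to be entered on the eCRF and do not mention non-serious ones.

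**What happens before the first dose.** CSF is withdrawn and the product then infused in one LP (7.1.2.2). For the 20 mL dose, if 15 mL of CSF cannot be collected, the investigator may "ask the subject to return on the following day for a second attempt after additional hydration". The alternatives are to skip that visit's dose (Part 2, 11.2.2) or to discontinue the subject (Part 1, 11.1.2; Part 2 if no dose has yet been given). At any dose, an LP may return no CSF after two attempts.

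**Who is analysed.** SAP 6.2: "The Safety Population will consist of all subjects treated with at least one dose of study treatment". Protocol 15.6 agrees.

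**End of recording.** Protocol 14.2.5 records Part 1 non-serious events "from the time of first dose through subject completion of the study up to 28 days post-dose". At Visit 5, Day 29 ± 4, "Subjects will undergo lumbar puncture for CSF collection for PK assessments" (11.1.5). Section 14.1, written for both Parts, says "TEAEs will be limited to those events occurring within 28 days after the last visit", as does the synopsis. Section 15.11 ends Part 1 treatment-emergent events at Day 29/ET. SAP 8.8.2 ends them 28 days after the last injection and calls anything later post-treatment.

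**The concern.** The protocol treats the LP as a hazard in its own right. Section 5.3 names post-LP headache and back pain as the commonest LP events, 14.2.3 makes LP events adverse events of special interest, and 14.2.5.2 has each event rated separately for relation to the product and to the LP. Safety is a primary objective in both Parts.

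The recording and analysis windows are nevertheless set by the drug. An event filed as medical history, or arising after the window closes, receives no LP-causality rating and reaches no table of special-interest or LP-related events. What is at stake is the completeness of the non-serious LP harm count at two points: before the first dose, and after the last puncture.

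**Working it through.** **1. Start.** Needle placement and CSF withdrawal precede the infusion, so the unrecorded interval is:
- successful first LP: minutes, within the same procedure;
- failed first LP with a next-day retry: about 1 day;
- Part 2 Visit 2 dose skipped and next attempted at Visit 3, if 11.2.2 is read as allowing this: nominally 21 − 1 = 20 days;
- never dosed: no recording at all, and no place in the Safety Population.

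SAP 8.8.2 classifies events by date, on or after the date of first dose. A same-day pre-infusion event would therefore count as treatment-emergent if it were entered, but the footnotes send it to medical history. After a next-day retry, the day of the failed attempt becomes Day −1 (SAP 7.1), so an event on that day precedes treatment under both documents.

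**2. End of Part 1.** SAP 7.1 numbers days as (date − Day 1 date) + 1, so 28 days post-dose is Study Day 28 + 1 = 29. This reproduces the Day 29/ET in Protocol 15.11. Days of recording left after the last LP = 29 − LP day:

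| Day of last LP | 25 | 26 | 27 | 28 | 29 | 30 | 31 | 32 | 33 |
|---|---|---|---|---|---|---|---|---|---|
| Further days | 4 | 3 | 2 | 1 | 0 (same day only) | −1 | −2 | −3 | −4 |

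Part 1 schedules LPs on Days 1, 2, 4, 8 and 29: 5 × 24 = 120, of which 24 (20%) are the last. Twenty-four is a ceiling: an event is lost only if its onset is after Day 29.

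**3. The end rules side by side (nominal days).**

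| Source | Part 1 end | Part 2 end |
|---|---|---|
| Protocol 14.1 (TEAE) | 29 + 28 = Day 57 | 253 + 28 = Day 281 |
| Protocol 14.2.5 (AE recording) | Day 29 | Day 281 |
| Protocol 15.11 (TEAE) | Day 29/ET | Day 281 |
| SAP 8.8.2 (TEAE) | 1 + 28 = Day 29 | 104 + 28 = Day 132 |

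**4. Part 2 Day 253 LP.** It falls 253 − 104 = 149 days after the nominal last injection. With the visit windows (± 7 and ± 5 days) the gap is at least 246 − 109 = 137 days, always beyond 28. Events after it are recorded under 14.2.5 up to Day 281, but SAP 8.8.2 makes them post-treatment, so they miss its LP-related TEAE tables. Up to 32 LPs are concerned; an early-termination LP within 28 days of an injection would be partly covered.

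**The case against.** The strongest reply is that most LP harm is captured. Once the first dose is given, recording continues. Part 1 LPs on Days 2, 4 and 8, and failed or pre-dose LPs at Part 2 Visits 3 to 7 after a first dose, are covered and rated for LP relatedness. Subjects are monitored after the LP as well as after the dose (11.1.2, 11.2.2), and 14.2.5 asks for all observed or reported events. Both documents have a pre-treatment event category, and medical history is coded and summarised (SAP 8.4.2). The 15 mL rule applies only to the 20 mL dose, which in Part 1 is Cohort 4, 6 subjects. All of this stands and narrows the point. It does not remove it: the footnotes still direct non-serious pre-dose events away from AE collection, and the never-dosed subject stays outside the Safety Population.

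On the Part 1 end, the wording of 14.2.5 and the label Day 29/ET could be stretched to a late Visit 5, post-LP vital signs are taken that day, and serious events run to 28 days after completion. That makes the close ambiguous for Days 30 to 33, but gives no clear cover for later onset.

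Stronger readings that a reader might reach are not supported:
- **All failed or non-dosing LPs go uncounted.** At the start, the gap exists only before the first dose.
- **LP-related events need not be followed up.** The sentence "For AEs with a causal relationship to the investigational product, follow-up by the investigator is required until the event or its sequelae resolve" invites this, but 14.2.5 also has the outcome of every event pursued, and events monitored until resolved or stable, whatever the cause.
- **Day 253 LP harm is not recorded.** It is, for 28 days. The absence of a scheduled contact afterwards is not a recording gap.
- **The comparison of arms is biased.** Both Part 2 arms have the same LP schedule, and no such bias is shown.

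**Conclusion.** The concern holds in a limited form.

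- **Start:** non-serious harm with onset before the first dose is filed as medical history, and subjects punctured but never dosed drop out of the safety analysis. The size is unknown because the documents give no LP failure rate.
- **Part 1 end:** recording closes on the nominal day of the last LP, leaving between 4 days and none, with an LP on Days 30 to 33 after closure. At most 24 of 120 scheduled LPs are affected. This assumes full enrolment of 24 and a literal reading of 14.2.5 and 15.11.
- **Conflict:** the end rules give Day 29 or Day 57 in Part 1 and Day 132 or Day 281 in Part 2. The SAP's choice keeps events after up to 32 Day 253 LPs out of the LP-related tables although they are recorded.

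Serious events are not part of the collection gap at either end. It would go too far to conclude that the delivery route will look materially safer than it is, since no event or failure rate supports a size. The correction is still worth making, because LP harm falls under a primary objective and the change is small.

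**What to change.** 1. In Protocol Table 5 footnote 13, Table 6 footnote 12 and section 14.2.5, record non-serious adverse events from the start of the first LP attempt.
2. Reconcile Protocol 14.1, 14.2.5 and 15.11 and SAP 8.8.2 to one end rule that covers the last LP. The 28 days after the last visit already in 14.1 would do. Changing 14.2.5 alone is not enough, because the cutoffs in 15.11 and SAP 8.8.2 would still keep the events out of the tables.
3. In the SAP, tabulate LP-related adverse events for all subjects with an LP attempt, dosed or not, including events after non-dosing LPs. SAP 8.8.2 now plans LP-related tables for Part 2 only.

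A telephone call after the final LP is optional; similar calls already exist on Part 1 Days 5 to 7 and Part 2 Days 8 and 137.

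The cost is somewhat longer Part 1 recording (nominally to Day 57 instead of Day 29), wording changes in both documents, and one extra table. Where collection is already complete, the SAP changes can still be applied to events that were recorded.

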# 3. LIST OF ABBREVIATIONS AND DEFINITIONS OF TERMS

The following abbreviations and specialist terms are used in this study protocol.

 Table 7:
 Abbreviations and Specialist Terms (Study RNX-AX204-101)

Abbreviation or Specialist Term	Explanation
ADA	Anti-drug antibodies
ADL	Activities of daily living
AE	Adverse event
AESI	Adverse events of special interest
AIS	American Spinal Injury Association Impairment Scale
ANCOVA	Analysis of Covariance
BMI	Body mass index
BPI	Brief Pain Inventory
BUN	Blood urea nitrogen
СМН	Cochran-Mantel-Haenszel
CNS	Central nervous system
CRO	Contract research organization
CSCI	Chronic Spinal Cord Injury
CSF	Cerebrospinal fluid
CTCAE	Common Terminology Criteria for Adverse Events
CUE-Q	Capabilities of Upper Extremity – Questionnaire
ECG	Electrocardiogram
eCRF	Electronic case report form
EDC	Electronic data capture
eGFR	Estimated Glomerular Filtration Rate
ER	Emergency room
ET	Early termination
FAS	Full analysis set population
FDA	Food and Drug Administration
GCP	Good Clinical Practice
GRASSP	Graded Redefined Assessment of Strength, Sensation and Prehension
HED	Human equivalent dose
HIV	Human immunodeficiency virus
ICF	Informed Consent Form
ICH	International Conference on Harmonization
DSMB	Data and Safety Monitoring Board

Abbreviation or Specialist Term	Explanation
IEC	Independent Ethics Committee
IRB	Institutional Review Board
IRT	Integrated response technology
ISAFSCI	International Standards to document remaining Autonomic Function after Spinal Cord Injury
ISNCSCI	International Standards for Neurological Classification of SCI
LP	Lumbar Puncture
LSMean	Least Square Means
MEP	Motor Invoked Potentials
MRI	Magnetic Resonance Imaging
MTD	Maximum Tolerated Dose
NOAEL	No Observed Adverse Effect Level
NOEL	No Observed Effect Level
OAE	Other significant adverse event
PACU	Post-Anesthesia Care Unit
PGIC	Patient's Global Impression of Change
PI	Principal Investigator
РК	Pharmacokinetics
PRN	Pro re nata (as needed)
QoL	Quality of Life
QTcF	QT interval using Fridericia Correction Formula
SAE	Serious adverse event
SCIM III	Version III of the Spinal Cord Independence Measure
SF-36	Short Form - 36 v2 Health Survey
SNRI	serotonin norepinephrine reuptake inhibitor
SOC	system organ class
SSRI	selective serotonin reuptake inhibitor
TEAE	treatment-emergent adverse event
TNF	tumor necrosis factor
UEMS	upper extremity motor score
UMC	Uppsala Monitoring Centre
US	United States
WHO	World Health Organization

## 4. INVESTIGATORS AND STUDY PERSONNEL

This study will be conducted by qualified investigators under the Sponsorship of ReNetX Bio, Inc. (the sponsor) at approximately 5 investigational centers in the United States.

The contact information for the Medical Monitor along with the telephone numbers of the other contact persons for the sponsor are listed in Table 1. Contact information for the designated Contract Research Organization, (CRO), and other vendors are listed in the Investigator Site File provided to each site.

# 5. INTRODUCTION

# 5.1. AXER-204, a Human NoGo Trap Fusion Protein

Mammalian brain and spinal cord networks stabilize during development, such that axonal growth in the adult CNS is either non-existent or extremely limited. After adult CNS injury, the extracellular factors that maintain axonal stability restrict axonal growth and permit only severely limited recovery of function. Adult extracellular axonal growth inhibitors include a group of proteins from the oligodendrocyte, Nogo-A, MAG, OMgp, and ephrin-B3, which interact with axonal receptors, including NgR1, NgR2, PirB, and EphA4 [Liu 2006, Schwab 2014]. Extracellular proteoglycans, containing chondroitin sulfates, also inhibit axonal sprouting in the adult CNS, particularly near sites of astrogliosis and scar formation [Ohtake 2015, Sharma 2012]. There is substantial molecular cross talk between ligands and receptors. The key inhibitory ligands Nogo, MAG, and OMgp all bind and activate NgR1 on axons to inhibit axonal extension. Likewise, PirB (LILRB2) has been found to bind Nogo, MAG, and OMgp and to mediate axonal growth inhibition. Consistent with partially overlapping roles in axonal inhibition, simultaneous genetic deletion of Nogo, MAG, and OMgp has greater impact on axonal growth and functional recovery following CNS injury than deletion of a single inhibitor [Cafferty 2010]. A representation of the role of Nogo, MAG, and OMgp and other key regulators of axonal growth in the adult CNS is presented in Figure 1.

#### Figure 1: Key Components Regulating Axonal Growth in the Adult Mammalian Central Nervous System

Targeting one ligand or one receptor in the inhibitory adult CNS pathways has been shown to yield some benefit in certain specific pre-clinical spinal cord injury (SCI) models. Based on these observations, anti-Nogo antibodies are entering clinical trials for new (subacute) SCI. In distinction, NoGo Trap (AXER-204, Nogo Receptor decoy, hNgR1(310)ecto-Fc Ala Ala)

represents a mechanistically superior approach to promoting axonal growth following injury as it binds three key inhibitors, Nogo, MAG, and OMgp, and blocks their interaction with endogenous NgR1 and other receptors (Figure 2). Consistent with this mechanism, NoGo Trap has been shown in multiple laboratories to promote axonal growth and recovery of function in a variety of pre-clinical models of CNS injury including stroke [Lee 2004], dorsal root crush injury [Harvey 2009], acute transection SCI [Li 2004], and acute/sub-acute contusion SCI [Ji 2006, Wang 2006, Wang 2014]. Most critically, NoGo Trap supports axonal growth and functional recovery in chronic contusion SCI [Wang 2011], while no other blocker of extrinsic signals has reported efficacy in this setting. Recent pre-clinical studies have shown that intrathecal lumbar administration results in broad CNS distribution in rat and non-human primate and that intermittent intrathecal bolus injection of the protein provides equivalent restoration of function in rat contusion SCI in comparison to previously obtained results employing continuous infusion [Wang 2014]. AXER-204 promotes corticospinal axon growth and the use of the impaired forelimb during spontaneous feeding and the impaired hindlimb during locomotion non-human primates with cervical hemisection SCI [Wang 2020].

